1 INTRODUCTION

This document details the planned statistical analyses for Pliant Therapeutics Inc, protocol “PLN-74809-IPF-205” study titled “A Phase 2a, randomized, double-blind, placebo-controlled evaluation of PLN-74809 on type 1 collagen deposition using ⁶⁸Ga-CBP8 PET/MRI imaging in participants with idiopathic pulmonary fibrosis (IPF)”. The proposed analyses are based on the contents of Amendment 1 of the protocol (dated 04 Oct 2021). Any changes made from the planned analysis described in the protocol or after finalization of this SAP will be documented in the Clinical Trial Report (CTR).

This is a Phase 2a, single-center, randomized, double-blinded, placebo-controlled study to evaluate type 1 collagen deposition in the lungs following once-daily treatment with 160 mg PLN-74809 for 12 weeks in participants with IPF. The study consists of an up to 28-day screening period, a 12-week treatment period, and a 2-week (± 3 days) post treatment follow-up period.

2 STUDY OBJECTIVES, ENDPOINTS, AND ESTIMANDS

2.1 Objectives

Primary objective:

- Quantification of type 1 collagen in the lung following 12 weeks of treatment with PLN-74809, as assessed by changes from baseline in ⁶⁸Ga-CBP8 positron emission tomography (PET)/ magnetic resonance imaging (MRI) tracer uptake patterns

Secondary objective:

- Assessment of the safety and tolerability of PLN-74809 in idiopathic pulmonary fibrosis (IPF) participants

Exploratory objectives:

- Relationships between PLN-74809 systemic exposure, PET imaging and biomarkers in IPF participants
- Forced vital capacity (FVC): absolute FVC volume and FVC as percent of predicted as assessed by spirometry
- Patient-reported outcome (PRO): a visual analog scale (VAS) for cough severity

QMD Ref. [REDACTED]	Governing QMD: [REDACTED]
Confidentiality Statement	
This document is the property of [REDACTED] without prior approval from [REDACTED]	and may not be duplicated, copied, altered or removed from company or in compliance with [REDACTED]

		Controlled Quality Management Document
	Sponsor:	Pitant Therapeutics Inc
	Protocol Number:	PLN-74809-IPF-205
STATISTICAL ANALYSIS PLAN		

2.2 Endpoints

2.2.1 Primary Endpoints

The primary pharmacodynamic endpoint of this study is the whole lung standardized uptake value (SUV).

2.2.2 Secondary Endpoints

The secondary safety endpoints are:

- Treatment emergent AEs and SAEs
- Clinical laboratory parameters, including hematology, serum chemistry, coagulation, and urinalysis
- ECG
- Vital signs measurements
- Concomitant medications

2.2.3 Exploratory Endpoints

Plasma PLN-74809 concentrations (total and unbound) and percent unbound PLN-74809 at each sampling time point will be presented in listings and summarized by day with descriptive statistics. Plasma PLN-74809 versus time profiles (with plasma concentrations on both a log and linear scale) will be plotted for each participant. In addition, the following PLN-74809 PK parameters will be estimated on Day 1:

- C_{max} : Maximum observed plasma concentration
- AUC_{0-6h} : Area under curve (AUC) from the time 0 to 6 hours postdose
- T_{max} : Time to reach C_{max}
- $C_{max,ub}$: Maximum observed unbound plasma concentration
- $AUC_{0-6h,ub}$: Unbound AUC from the time 0 to 6 hours postdose

The exploratory pharmacodynamic or efficacy endpoints are:

- Markers of fibrosis: Pro-peptide of Type III Collagen (PRO-C3), CTX-III_HP, and Integrin Beta 6(ITGB6)
- Absolute forced vital capacity (FVC) by volume (mL) and percent predicted (%)
- PRO: a VAS for cough severity

3 SAMPLE SIZE

QMD Ref. [REDACTED]	Governing QMD: [REDACTED]
Confidentiality Statement	
This document is the property of [REDACTED] without prior approval from [REDACTED]	and may not be duplicated, copied, altered or removed from company or in compliance with [REDACTED]
REF: [REDACTED]	

		Controlled Quality Management Document	
		Sponsor:	Pliant Therapeutics Inc
		Protocol Number:	PLN-74809-IPF-205
STATISTICAL ANALYSIS PLAN			

The sample size of approximately 12 participants (8 participants receiving 160 mg PLN-74809 and 4 receiving placebo) is expected to provide a meaningful evaluation of PLN-74809 safety, tolerability and pharmacokinetics (PK) in the target population and add to the data of approximately 21 participants planned to be evaluated at this dose level in an ongoing multicenter, dose-ranging Phase 2a study (PLN-74809-IPF-202).

4 RANDOMIZATION

Approximately 12 eligible participants will be randomized in a 2:1 ratio (160 mg PLN-74809 vs placebo). Randomization will be stratified by use of standard-of-care IPF therapy (pirfenidone or nintedanib) (yes or no).

5 PLANNED ANALYSES

The Statistical Analysis Plan (SAP) and Table, Figure, Listing (TFL) Shells (and any amendments) must be approved prior to database lock. If, post database lock, additional statistical analyses or changes to the statistical analysis are required, then such additional analyses will be documented in a Post Database Lock Statistical Analysis Plan Addendum.

5.1 Analysis Sets

5.1.1 Screened Population

The screened population includes all participants screened who gave informed consent.

5.1.2 Intent-to-Treat Population

The intent-to-treat (ITT) population includes all randomized participants. Treatment assignment is by randomized treatment.

5.1.3 Safety Population

The safety population includes all randomized participants who received at least one dose of study drug. Treatment assignment is by actual treatment.

5.1.4 Pharmacokinetic (PK) Analysis Population

The PK analysis population includes all randomized participants who have sufficient PLN-74809 concentration data for PK calculation. Treatment assignment is by actual treatment.

QMD Ref: [REDACTED]	Governing QMD: [REDACTED]
Confidentiality Statement	
This document is the property of [REDACTED] without prior approval from [REDACTED]	and may not be duplicated, copied, altered or removed from company [REDACTED] or in compliance with [REDACTED]
REF: [REDACTED]	

		Controlled Quality Management Document
		Sponsor: Pliant Therapeutics Inc
		Protocol Number: PLN-74809-IPF-205

5.1.5 Pharmacodynamic (PD) Population

The PD population includes all randomized participants who received any amount of study drug and who have results from baseline and from at least one post-baseline PET/MRI scan or PD assessment. Treatment assignment is by actual treatment.

5.2 Derived Data

This section describes the derivations required for statistical analysis. Unless otherwise stated, variables derived in the source data will not be recalculated.

5.2.1 Race

Where more than one race category has been selected for a participant, these race categories will be combined into a single category labelled “Multiple Race” in the summary tables. The listings will reflect the original selected categories.

5.2.2 Body Mass Index

Body mass index (BMI) will be calculated as follows:

BMI (kg/m^2) = Weight at Screening (kg) / [Height at Screening (m) 2]

5.2.3 GAP Index and Staging System

The GAP index and staging system is a multidimensional prognostic staging system derived from four commonly measured clinical and physiologic variables (Gender, Age and two lung physiology variables [FVC and DLCO]). Points are allocated to each clinical or physiological variable and points are summed to provide a total score (from 0 to 8). The total score is then used to assign a GAP stage (I, II, or III) as follows:

QMD Ref: [REDACTED]	Governing QMD: [REDACTED]
Confidentiality Statement	
This document is the property of [REDACTED] without prior approval from [REDACTED]	and may not be duplicated, copied, altered or removed from company or in compliance with [REDACTED]
REF: [REDACTED]	Page 9 of 37

		Sponsor: Pliant Therapeutics Inc Protocol Number: PLN-74809-IPF-205
STATISTICAL ANALYSIS PLAN		

GAP Scoring

Predictor	Points Allocated
Gender	Female = 0 Male = 1
Age	≤ 60 = 0 $61 - 65$ = 1 > 65 = 2
Physiology - FVC, % Predicted	> 75 = 0 $50 - 75$ = 1 < 50 = 2
Physiology - DLCO, % Predicted	> 55 = 0 $36 - 55$ = 1 ≤ 35 = 2 *Cannot perform = 3
Total Point Score	0-8

* 'Cannot perform' is only assigned if symptoms or lung function prohibited performance of the DLCO maneuver. If DLCO is unavailable for a non-respiratory reason (eg, an operational reason), the GAP index and staging system cannot be applied.

GAP Staging System

Stage	I	II	III
Points	0-3	4-5	6-8

The screening assessments will be used to determine GAP stage.

5.2.4 Standardized Uptake Values

Standardized uptake values (SUVs) will be quantified, using MIMs software as specified in the protocol, for each lung (left and right) and by 6 regions (lower subpleural, lower central, middle subpleural, middle central, upper subpleural, and upper central) as well as whole lung, by the Imaging laboratory from the PET scans. Multiple SUV parameters will be provided for each region. The following parameters will be provided for each region, each lung, and for the whole lung:

- SUVmean: mean of the SUVs for each region in each lung
- SUVmax: maximum of the SUVs for each region in each lung
- SUVtopquartile: mean of the SUVs within the top quartile of each region in each lung

QMD Ref: [REDACTED]	Governing QMD: [REDACTED]
Confidentiality Statement	
This document is the property of [REDACTED] without prior approval from [REDACTED]	and may not be duplicated, copied, altered or removed from company or in compliance with [REDACTED]

		Controlled Quality Management Document Sponsor: Pliant Therapeutics Inc Protocol Number: PLN-74809-IPF-205
STATISTICAL ANALYSIS PLAN		

The mean of both lungs will be constructed as follows:

Region SUV metric = (left region SUV metric + right region SUV metric)/2

Whole lung SUV metric = (left whole lung SUV metric + right whole lung SUV metric)/2

5.2.5 Baseline and Change from Baseline

Baseline is defined as the last nonmissing value (either scheduled, unscheduled or repeat) before the participant received the first dose of study drug. The baseline value of the VAS is assumed to be collected in Visit 3 (Day 1). Change from baseline is defined as the difference between baseline and any post-baseline records.

5.2.6 Percent Change from Baseline

Percent change from baseline will be calculated as change from baseline multiplied by 100 then divided by the baseline value.

5.2.7 Early Terminations Assessments

Early Termination (ET) assessments will not be summarized unless the ET visit falls on a scheduled visit. ET assessments will be listed only.

5.2.8 Unscheduled Visits

Only scheduled post-baseline values will be tabulated unless otherwise stated. Post-baseline repeat / unscheduled assessments will be included in all listings in the relevant appendices of the CTR.

5.2.9 Duration / Study Day / Time

Study day will be calculated as the number of days from first dose of study drug

- date of event – date of first dose of study drug + 1, for events on or after first dose
- date of event – date of first dose of study drug, for events before first dose

5.2.10 Conventions for Missing and Partial Dates

Dates (historical or during study conduct) will only be imputed if a full date is needed for a calculation or to support a definition.

QMD Ref: [REDACTED]		Governing QMD: [REDACTED]
Confidentiality Statement		

This document is the property of [REDACTED], and may not be duplicated, copied, altered or removed from company without prior approval from [REDACTED] or in compliance with [REDACTED].

		Controlled Quality Management Document
	Sponsor:	Pliant Therapeutics Inc
	Protocol Number:	PLN-74809-IPF-205
STATISTICAL ANALYSIS PLAN		

All dates presented in the individual participant listings will be presented as recorded on the electronic case report form (eCRF).

Missing / Partial Start / Stop Date of Adverse Events, Medical History and Concomitant Medication

Missing and partial start dates will be imputed solely for the purpose of determining whether an AE is treatment-emergent, medical history is ongoing at screening, or a medication is concomitant to study drug.

Partial or missing stop date will be imputed as follows:

If the stop date is completely missing and the event has resolved, or the participant has stopped taking the concomitant medication, the stop date will be imputed as the date of the participant's last clinic visit in the study.

- If only the year is known, the stop date will be imputed as "31-Dec" of that year or as the date of the participant's last clinic visit in the study if in the same year.
- If the month and year are known, the stop date will be imputed as the last day of that month unless the stop date corresponds to the same month as the participant's last clinic visit in which case the date of participant's last clinic visit in the study will be used instead.

Missing start date will be imputed as follows:

- If the stop date occurs on or after the start of study drug or the event / concomitant medication is ongoing, the start date will be imputed as the date of the first dose of study drug.
- If the stop date occurs before the start of study drug, the start date of the event / concomitant medication will be imputed as the participant's screening date or the stop date of the event / concomitant medication whichever the earlier.

Partial start date (year present, but month and day missing)

- If the stop date occurs on or after the start of study drug or the event / concomitant medication is ongoing, and the year is the same as the year of first dosing, the start date will be imputed as the date of the first dose of study drug. If the year is different from the year of first dosing, "01-Jan" will be used.
- If the stop date occurs before the start of study drug, the start date of the event / concomitant medication will be imputed as the "01-Jan" of the same year.

Partial start date (month and year present, but day missing)

- If the stop date occurs on or after the start of study drug or the event / concomitant medication is ongoing, the start date will be imputed as the first day of the same month and year unless this partial start date is in same month as the first dose of study drug in which case the date of first dose of study drug will be used.

QMD Ref. [REDACTED]	Governing QMD: [REDACTED]
Confidentiality Statement	
This document is the property of [REDACTED] and may not be duplicated, copied, altered or removed from company without prior approval from [REDACTED] or in compliance with [REDACTED]	

		Controlled Quality Management Document	
		Sponsor:	Pliant Therapeutics Inc
		Protocol Number:	PLN-74809-IPF-205
STATISTICAL ANALYSIS PLAN			

- If the stop date occurs before the start of study drug, the start date will be imputed as the first day of the month and year of the partial stop date.

If the start time is missing it will be imputed only in the case where the start date of the concomitant medication / event corresponds to the date of the first dose of study drug. The time will be imputed as the same time as the first dose of study drug. In all other cases the time will not be imputed.

Missing Date of Last Dose

If date of last dose is not present, the date of completion/termination will be imputed as the date of last dose for the calculation of study drug exposure.

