5.6 Baseline Comparability

The comparability of treatment groups with respect to participant demographics and baseline characteristics will be assessed in a descriptive manner, but no formal statistical testing will be performed.

Standard continuous or categorical variable summaries will be presented by randomized treatment group for the following variables based on the safety population.

QMD Ref. [REDACTED]		Governing QMD: [REDACTED]
Confidentiality Statement		
This document is the property of [REDACTED] without prior approval from [REDACTED]		and may not be duplicated, copied, altered or removed from company or in compliance with [REDACTED]

		Controlled Quality Management Document
	Sponsor:	Pliant Therapeutics Inc

		STATISTICAL ANALYSIS PLAN
--	--	----------------------------------

Demographic characteristics include:

- Age at Informed Consent (years)
- Sex
- Fertility Status for Women
- Ethnicity
- Race
- Weight at screening (kg)
- Height at screening (cm)
- Body Mass Index at screening (kg/m²)
- Duration of IPF diagnosis (months), defined as the number of months from start date of first date reported for medical history preferred term ‘idiopathic pulmonary fibrosis’ to first dose of study drug
- Participant taking nintedanib or pirfenidone at screening
- Duration of nintedanib or pirfenidone use (months), defined as the number of months from start date of usage of nintedanib or pirfenidone to first dose of study drug
- GAP stage

A listing of demographic characteristics at baseline will be provided.

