5.7 Medical History

A summary of previous and ongoing conditions at screening will be presented by randomized treatment group and overall for the safety population. All reported medical history data will be listed. Non-pharmacological procedures will be provided as a separate listing.

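### SAP 5.2.10 has no exception for medical history already resolved at screening or medication already stopped before first dose, so its stop-date rule can put such records in the wrong class

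*SAP*

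**What the plan says.** The rule stands under a single heading, "Missing / Partial Start / Stop Date of Adverse Events, Medical History and Concomitant Medication", so all three record types share it. For a completely missing stop date it reads "If the stop date is completely missing and the event has resolved, or the participant has stopped taking the concomitant medication", then "the stop date will be imputed as the date of the participant's last clinic visit in the study". If only the year is known, the date becomes 31 December, or the last visit when that falls in the same year. If month and year are known, it becomes the end of the month, or the last visit when that falls in the same month.

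Two sentences limit the use of imputation. The general one is "Dates (historical or during study conduct) will only be imputed if a full date is needed for a calculation or to support a definition". The second, worded for start dates only, restricts them to "determining whether an AE is treatment-emergent, medical history is ongoing at screening, or a medication is concomitant to study drug". Listings show dates as recorded.

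The resulting classes feed two descriptive outputs. SAP 5.7 says "A summary of previous and ongoing conditions at screening will be presented by randomized treatment group and overall". SAP 5.8 defines prior medication as started and stopped before first dose, and concomitant medication as taken on or after that date.

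The last start-date rule covers a start with known month and year and a stop before first dose. It says "the start date will be imputed as the first day of the month and year of the partial stop date".

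**The concern.** The last-visit default suits adverse events and drugs taken on study, where the end must fall within follow-up. It does not suit records whose end is already known to lie before the study. Protocol 7.2 and the Schedule of Events place medical history at screening, so a condition recorded there as resolved had ended by then. Protocol 6.6.1 collects at screening the medications of the preceding 30 days, so some will have stopped before first dose. The rule names no exception for either.

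At stake is the accuracy of the medical history and prior/concomitant medication tables. SAP 2.2.2 lists concomitant medications among the secondary safety endpoints, so the second table is more than background.

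**Working it through.** The plan states no figure to reproduce. The check applies the rules of SAP 5.2.10 and the definitions of SAP 5.7 and 5.8 to typical records.

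**Why the direction is fixed.** First dose is taken in clinic at Visit 3 (Protocol Appendix 1), so for a dosed participant the last clinic visit cannot precede first dose, and first dose follows screening. An imputed stop at the last visit therefore always falls after screening and never before first dose.

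**Assumed calendars.** The documents give no dates, so two were assumed, each with first dose 28 days after screening and the last visit 98 days after first dose:
- A: screening 10 May 2022, first dose 7 Jun 2022, last visit 13 Sep 2022.
- B: screening 18 Oct 2022, first dose 15 Nov 2022, last visit 21 Feb 2023.

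**Test used.** History is ongoing if start ≤ screening ≤ stop. A drug is prior if start and stop both precede first dose. Rows 1 to 5 are resolved or stopped records. Apart from row 2, their start is known and lies three years back.

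| Record | Imputed stop, A | Imputed stop, B | History class | Drug class |
|---|---|---|---|---|
| 1. Stop missing | 13 Sep 2022 | 21 Feb 2023 | ongoing | concomitant |
| 2. Start and stop missing | 13 Sep 2022 | 21 Feb 2023 | starts after screening | concomitant |
| 3. Stop year 2020 | 31 Dec 2020 | 31 Dec 2020 | not ongoing | prior |
| 4. Stop year 2022 (screening year) | 13 Sep 2022 | 31 Dec 2022 | ongoing | concomitant |
| 5. Stop month two months before first dose | 30 Apr 2022 | 30 Sep 2022 | not ongoing | prior |
| 6. Drug started on study, stop missing | 13 Sep 2022 | 21 Feb 2023 | n/a | concomitant |

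Rows 1 and 4 are wrong for any record that had ended before screening (history) or before first dose (drug). In row 2 the missing start becomes the first-dose date, so the condition counts as neither previous nor ongoing at screening. Rows 3, 5 and 6 are right. One limit on row 4: if screening and first dose straddle a year end, 31 December of the screening year precedes first dose and the drug stays prior, but the history error remains.

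**Size per record.** With the planned arms of 4 and 8, one participant is 1/4 = 25 points on placebo and 1/8 = 12.5 points on PLN-74809. Both are ceilings: SAP 5.3.3 counts a participant once per term, so the full shift needs a participant with no other record in that row.

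**Start-date rule.** On calendar A, take a condition starting in March 2022 and stopping on 5 June 2022, before first dose. The rule gives a start of 1 June 2022, discarding the known month; and since this stop date is complete, there is no partial stop date to refer to. Prior or treatment-emergent status cannot change, because the stop precedes first dose either way. Ongoing-at-screening status changes only when the stop month is later than the screening month, as here (1 June is after 10 May). That is rare.

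**The case against.** The strongest reply is that imputation may never be triggered. SAP 5.2.10 imputes only where a full date is needed, and a condition recorded at screening as resolved can be classed from that status alone. The eCRF is not among the documents, so this cannot be excluded. But the rule fires only once the record is known to be resolved or stopped, then assigns a date that can contradict that status, and nothing says that status takes precedence.

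Other points stand and limit the finding:
- A reader might infer that every unknown stop date leads to a wrong class. It does not: most partial dates, and drugs stopped on study, are classed correctly. Where timing is truly unknown, counting a drug as concomitant is a cautious choice.
- A reader might picture drugs stopped years ago appearing as concomitant. The 30-day collection window in Protocol 6.6.1 makes that unlikely; with screening of up to 28 days, the realistic window is about 30 + 28 = 58 days before first dose.
- A reader might carry the imputed start into SAP 5.6, "Duration of nintedanib or pirfenidone use (months), defined as the number of months from start date of usage", and obtain a duration of 0 months. The restriction of start-date imputation to three classifications excludes this, because durations are not among them.
- SAP 5.7 does not say that previous and ongoing conditions are tabulated separately, so a changed class may move no cell of that table.
- A disallowed drug shown wrongly as concomitant could be checked against the listings, and Protocol 6.6.2 already bars such drugs for at least 30 days before screening.

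**Conclusion.** The point holds as a minor one. On a literal reading, the shared rule gives the wrong class to history recorded at screening as resolved, and to medication stopped before first dose, when the stop date is completely missing. It does the same for a stop date known only to be in the screening year, subject to the year-end limit shown above. This is a stated rule with a wrong result, not a missing detail. The start-date wording is a separate slip with little practical effect.

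The conclusion assumes that class is decided by comparing dates and that recorded status does not override them. How many records are affected cannot be told from the documents. The documents do not support any inference that the primary result or the baseline comparison in SAP 5.6 is compromised: SAP 5.6 lists neither general medical history nor general concomitant medication.

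**What to change.** In SAP 5.2.10:

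1. For history recorded as resolved at screening, let the recorded status decide the class, and cap any imputed stop date at the screening date.
2. For medication recorded as stopped before first dose, cap the imputed stop date at the day before first dose. Keep the last-visit default where the timing is unknown.
3. In the last start-date rule, replace the reference to the partial stop date with the partial start date, so that a known start month is kept.

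The cost is a few lines of SAP wording and derivation code, with no new data. SAP section 5 requires amendments to be approved before database lock; a later change would go into the post-lock addendum described there.

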4.2 Inclusion Criteria

Each participant must meet the following criteria to be enrolled in this study:

1. Participants, aged 40 years or older
2. Diagnosis of IPF, within 8 years prior to screening, according to the American Thoracic Society (ATS)/ European Respiratory Society (ERS)/ Japanese Respiratory Society (JRS)/ Latin American Respiratory Society (ALAT) 2018 guidelines ([Raghu et al, 2018](#))

Note: If IPF diagnosis is within > 3 to ≤ 8 years at screening, the participant must have evidence of progression within the last 24 months, as defined by decline in FVC percent predicted based on a relative decline of $\geq 5\%$
3. FVC percent of predicted $\geq 45\%$; historical FVC for entry in the study is permitted if within 1 month of screening
4. Diffusing capacity for carbon monoxide (DLco) (hemoglobin-adjusted) $\geq 30\%$; historical DLco for entry in the study is permitted if within 1 month of screening
5. Participants currently receiving treatment for IPF with nintedanib or pirfenidone are allowed, provided these drugs have been given at a stable dose for at least 3 months before the Screening Visit and are expected to remain unchanged during the study (stable dose is defined as the highest dose tolerated by the participant during ≥ 3 months)
6. Estimated glomerular filtration rate ≥ 50 mL/min, according to the Cockcroft-Gault equation
7. Female participants of non-childbearing potential must be either surgically sterile or postmenopausal (refer to [Section 6.7.4](#))
8. Female participants of childbearing potential must use a contraceptive method with a failure rate of $<1\%$ per year or remain abstinent (refrain from heterosexual intercourse) during the treatment period and for 1 month after the last dose of study treatment (refer to [Section 6.7.4](#)).
9. Male participants with female partners of childbearing potential must agree to use contraceptive measures (refer to [Section 6.7.4](#)) or remain abstinent (refrain from heterosexual intercourse) during the treatment period and for at least 3 months after the last dose of study treatment.

10. Participants must agree to abstain from sperm or egg donation for the duration of the study, through to 3 months or 1 month, respectively, after administration of the last dose of study drug
11. Able to understand the purpose of the study and its procedures and to sign a written informed consent form (ICF)

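### SAP 5.2.10 dates some ongoing medical history to first dose, after screening, against its own stated purpose, and one bullet discards a known start month

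*SAP*

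**What the plan says.** The sub-heading in SAP 5.2.10 is "Missing / Partial Start / Stop Date of Adverse Events, Medical History and Concomitant Medication", so one set of rules serves three kinds of record. The section then limits what an imputed start may be used for. It begins "Missing and partial start dates will be imputed solely for the purpose of determining whether an AE is treatment-emergent" and completes the list with whether "medical history is ongoing at screening, or a medication is concomitant to study drug".

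For an item that is ongoing, or that stops on or after first dose, the rules are:

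- Start wholly missing: if "the event / concomitant medication is ongoing, the start date will be imputed as the date of the first dose of study drug".
- Only the year known: first dose if that is the dosing year, otherwise 1 January of the reported year.
- Month and year known: the first of that month, unless it is the dosing month, in which case first dose.

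For an item that stopped before study drug and whose start month and year are known, "the start date will be imputed as the first day of the month and year of the partial stop date".

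SAP 5.7 tabulates, by arm, the conditions that were previous or ongoing at screening. SAP 5.6 measures background therapy as the "number of months from start date of usage of nintedanib or pirfenidone to first dose of study drug" and gives no rule for a missing start. SAP 5.2.10 also opens with a broader sentence: "Dates (historical or during study conduct) will only be imputed if a full date is needed for a calculation or to support a definition".

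**The concern.** Moving an unknown start to first dose is the cautious choice for an adverse event, because it makes the event treatment-emergent. For medical history the question is different: was the condition there at screening? Screening comes before first dose, so an imputed start of Day 1 answers no for a condition that may have been present for years. The rule therefore works against one of the three purposes it is given.

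The bullet for items that stopped before study drug has another fault. It sits under the case where the start month and year are known, yet it builds the imputed date from the stop date.

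At stake is the accuracy of the medical-history table in a trial with planned arms of about 8 and 4, where a single participant is a large share of a row.

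**Working it through.** **1. Gap between screening and first dose.** Protocol 3.1 and Appendix 1 put screening at Day -28 to Day -1. SAP 5.2.9 counts a pre-dose day as event date minus first-dose date, so screening is 1 to 28 days before first dose.

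**2. Rules applied to an ongoing condition.** Take an illustrative first dose of 15 June 2022. Day -28 is then 18 May and Day -1 is 14 June.

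| Reported start | Imputed start | On or before 18 May? | On or before 14 June? |
|---|---|---|---|
| Wholly missing | 15 Jun 2022 | No | No |
| 2022 only | 15 Jun 2022 | No | No |
| June 2022 | 15 Jun 2022 | No | No |
| 2019 only | 1 Jan 2019 | Yes | Yes |
| Feb 2022 | 1 Feb 2022 | Yes | Yes |

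In the first three rows the imputed start is after screening whatever the screening day. In the June row, screening on 18 May gives no error, because a June start really is later than May; the error needs screening in the same month as dosing. Likewise, the year-only row errs only if screening falls in the dosing year. The last two rows come out right.

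**3. The other two purposes.** SAP 5.8 counts a drug as concomitant if it is taken on or after first dose, so an ongoing drug is concomitant whatever its start. An adverse event moved to first dose is treatment-emergent, which is the cautious direction.

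**4. The stop-month bullet.** Suppose a condition began in January 2022 (day missing) and stopped on 20 March, with screening on 28 February and first dose on 25 March (25 days later). Using the stop month gives 1 March. That is after screening, although the known start month is before it. This example has a complete stop date. If the stop is known only to the month M, SAP 5.2.10 sets it to the last day of M (or to the last clinic visit, if that falls in M). For a last-day stop to precede first dose, first dose must be in M+1 or later. For the imputed first of M to fall after screening, screening must be in M-1 or earlier. The gap is then at least the days in M plus 1, so at least 28 + 1 = 29 days, which exceeds 28. With a month-only stop the start month is still lost, but status at screening does not change.

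**5. Durations.** If a first-dose imputation were carried into SAP 5.6, duration would be 0 months. Protocol inclusion 5 admits users "provided these drugs have been given at a stable dose for at least 3 months before the Screening Visit", so the true minimum is (3 × 30.4375 + 1)/30.4375 = 3.03 months with screening on Day -1, and (3 × 30.4375 + 28)/30.4375 = 3.92 months on Day -28. Whether the plan permits that use is taken up below.

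**6. Size in the history table.** One participant wrongly absent from a row changes it by 1/8 = 12.5 percentage points in the active arm or 1/4 = 25 points in the placebo arm, at the planned numbers.

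**The case against.** The strongest reply is that the error may never reach a table. Protocol 7.2 has history recorded at screening, and an ongoing tick on the case report form could settle status without any imputation. No sentence says that a condition recorded at screening is dropped from the SAP 5.7 summary because of an imputed date. The bullets themselves speak of events and concomitant medication. Listings show dates as recorded, so a reader could see the problem. All of this limits the consequence. It does not remove the contradiction: the sub-heading and the purpose sentence both name medical history, and the SAP says the imputed start decides its status. If a form field governs instead, the SAP should say so.

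It is also fair to say that the stop-month bullet is probably a slip of one word, and that the March example applies a rule about a partial stop date to a complete one. Step 4 shows how much depends on that.

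A reader might go further and infer that an unknown start sets the duration of nintedanib or pirfenidone use to zero, which eligibility makes impossible. The documents do not support this. The purpose sentence restricts imputed starts to three uses, and duration is not one of them, so an unknown start leaves the duration missing. The opening sentence about dates needed for a calculation is broader, and the two should be reconciled, but no text sets a duration to zero. A figure for the resulting shift in an arm mean would also need an assumed true duration and an assumed number of users, since these drugs are optional.

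**Conclusion.** The point holds and is minor. Read literally, SAP 5.2.10 gives a Day 1 start to an ongoing condition whose start is wholly missing, year-only in the dosing year, or month-and-year in the dosing month. When the condition in fact pre-dates screening, it is classed as not ongoing at screening. It would be too wide to say this of every incomplete start, because partial starts in an earlier year or month are generally classified correctly. Separately, one bullet replaces a known start month with the stop month.

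The effect is confined to the descriptive medical-history summary. Medical history is not among the comparability variables listed in SAP 5.6, apart from the IPF date behind diagnosis duration, and it does not enter the SUV ANCOVA or the FVC MMRM. The conclusion assumes that programmers follow the text as written and that no form field overrides it. The documents do not say how many start dates will be incomplete, so the number of affected records is unknown.

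**What to change.** In SAP 5.2.10:

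- Keep first-dose imputation for adverse events and for the concomitant-medication flag.
- For medical history, let no imputed start fall later than the screening date, wherever the reported part of the date allows a start by then.
- In the bullet for a known start month and year with a stop before study drug, replace *stop* with *start*, so that the reported month is kept.

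In SAP 5.6, state that the durations of IPF and of nintedanib or pirfenidone use are calculated from reported dates only and are otherwise missing, in line with the sentence that limits the use of imputed starts. Imputing mid-points, or a fixed interval before screening, is not needed to cure the defect and would put assumed values into a variable the SAP does not impute.

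The cost is a few sentences and minor programming. A participant without a usable start date would have a missing duration.
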